## **ABSTRACT**

Many older adults suffer from derangements in skeletal muscle, including mitochondrial impairments, oxidative stress, insulin resistance, weakness, and fatigue. Despite evidence implicating inflammation in muscle dysfunction, a mechanistic link in the context of human aging is in early stages of investigation. The objective here is to determine how chronic inflammation influences exercise responsiveness, mitochondrial physiology, and metabolic function in skeletal muscle of older adults. Our central hypothesis is that chronic inflammation originating from inflamed adipose tissue triggers local inflammatory responses within skeletal muscle, leading to oxidative stress, reduced mitochondrial capacity, compromised muscle quality, functional and metabolic impairments, and attenuated adaptive responses to exercise. We will test this hypothesis through cross-sectional comparisons of older humans grouped by inflammation status. We will also perform a blinded, placebo-controlled study to determine if suppressing chronic inflammation using omega-3 fatty acids (n3-PUFA) restores skeletal muscle function and exercise responsiveness in older adults.

## **RESEARCH PLAN**

### **A. Specific Aims**

**Aim 1. To determine the impact of chronic inflammation on skeletal muscle physiology.**

**Hypothesis 1:** chronic inflammation triggers local inflammation within skeletal muscle, which provokes mitochondrial dysfunction, oxidative stress, protein damage, and functional impairments.

**Approach:** Skeletal muscle biochemical and functional parameters will be compared in older adults grouped into quartiles based on a composite systemic inflammatory score (CRP, IL-6, TNF- $\alpha$ ). Outcomes will be measured again following 26 weeks of placebo or n3-PUFAs to reduce adipose tissue inflammation.

**Aim 2. To determine the impact of chronic inflammation on responsiveness to acute exercise.**

**Hypothesis 2:** Acute exercise responsiveness is blunted in older adults with chronic inflammation, but restored when inflammation is reduced.

**Approach:** We will combine conventional molecular techniques with tracer-based approaches to evaluate anabolic and metabolic responses to a single bout of exercise in older adults grouped by inflammation status before and after inflammation is reduced by n3-PUFAs. Muscle and blood samples collected before and after a single bout of exercise will be used to measure anabolic and metabolic responsiveness to exercise from mRNA of exercise-responsive genes, activation of signaling proteins in muscle, and whole-body amino acid kinetics. Exercise-stimulated anabolic and metabolic responsiveness will be evaluated again after reducing inflammation in older adults (placebo vs. n3-PUFAs).

### **B. Background**

Many older adults suffer from derangements in skeletal muscle, including mitochondrial impairments, oxidative stress, insulin resistance, weakness, and fatigue. Exercise forestalls disease and disability in older adults, but many (15-20%) fail to demonstrate favorable adaptations even when interventions are painstakingly controlled (1-4). This so-called exercise resistance is particularly evident in older adults, who exhibit blunted anabolic responses to exercise and nutrition (5-7), which likely contributes to sarcopenia and attenuates adaptive responses to exercise. Early evidence shows that clearance of inflammatory cells in adipose tissue restores mitochondrial function and muscle mass in mice. In humans, we show that responsiveness to *acute* exercise is enhanced by omega-3 fatty acids (n3-PUFAs), putative suppressors of chronic inflammation, particularly in adipose tissue (8, 9). **Knowledge gap:** Despite evidence implicating inflammation in muscle dysfunction, a mechanistic link in the context of human aging is in early stages of investigation.

### C. Significance of Proposed Research

A goal of Healthy People 2020 is to improve the quality of life of older adults. The initiative underscores the importance of physical activity for metabolic health and preventing frailty. In this regard skeletal muscle health is critical, but muscle mass and strength are clearly compromised in older adults (10, 11). Sarcopenia is a major factor contributing to physical impairment with aging and predictive of disability (12). Exercise is a proven strategy to prevent and reverse sarcopenia, insulin resistance, and related complications (13, 14), but the recommended 150 minutes per week as a lifestyle goal is often met with poor adherence or is impractical for people with physical disability or other contraindications to exercise. There is also emerging evidence that the adaptations to exercise training are blunted in some people. For example, there is considerably variability in the improvement in cardiorespiratory fitness in response to a standardized aerobic training program (1, 2). These findings are in line with the concept of “anabolic resistance” whereby some individuals, particularly older adults, exhibit blunted increases in muscle protein synthesis in response to exercise or nutritional stimuli (3, 5, 6, 15, 16) and attenuated transcriptional responses to acute endurance exercise (4). Through a better understanding of the factors that attenuate exercise responsiveness, it may be possible to enhance adaptations to exercise in people who are “exercise resistant” or are unable to engage in exercise at sufficient intensities or volumes required to induce therapeutic benefit. Chronic inflammation appears to be a factor in exercise resistance based on observations that anabolic responses are restored when inflammation is reduced (17, 18). Altogether, precedent literature and our own preliminary data suggest that chronic systemic inflammation is detrimental to skeletal muscle and may limit adaptative responses to exercise. Inasmuch, targeting inflammation holds promise for enhancing responses to exercise, particularly under conditions of chronic inflammation such as sarcopenia, insulin resistance, type 2 diabetes, rheumatoid arthritis, and cancer cachexia. *The following contributions will emerge from the proposed work:*

- 1) *Identify mechanistic links between systemic inflammation, adipose tissue inflammation, and local inflammatory responses within aging muscle.*
- 2) *Determine the influence of inflammation on biochemical and functional parameters in aging muscle.*
- 3) *Determine if reducing inflammation can enhance the adaptations to acute exercise in older humans.*

*This contribution is significant because it will provide new fundamental knowledge to help understand the origins of metabolic and functional impairments in skeletal muscle*

*of older people and how chronic inflammation may be an effective target to enhance therapeutic benefits of exercise. Such knowledge would be expected to have a positive impact on health and quality of life of older adults.*

#### **D. Research Design and Methods:**

**Study Design:** Men and women between the ages of 20-35 years (N=30) and 65-85 years (N=120) will be recruited for this study. Participants in the older age group will be randomly assigned to receive n3-PUFA or placebo (corn oil) in a double-blind manner. Before and after the intervention, all participants will complete an outpatient study day (body composition, blood draw, treadmill test, strength test) and an inpatient study day (muscle biopsies, fat biopsies, indirect calorimetry, exercise test, mixed meal test) as described below in more detail. The DHA/EPA and placebo softgels will be supplied by Sancilio and Company, Inc., Riviera Beach, FL and stored in the Mayo Clinic Research Pharmacy at room temperature. During the intervention phase of the study, participants will be instructed to swallow 2 softgels twice per day with meals (morning and evening) for a total of 4 softgels per day. The DHA/EPA softgels will each contain 675mg of EPA and 300mg of DHA for a total daily dosage of 3.9g/day. The total omega-3 content of each capsule is 1050mg, which includes an additional 75mg of "non EPA/DHA" omega-3 fatty acids. The total fat content of the capsule will be 1200mg. This dose of EPA?DHA was chosen because it has been shown to augment the anabolic response of skeletal muscle [24] Every 4 weeks, participants will report to the Clinical Research and Trials Unit (CRTU) to pick up a new prescription and return any remaining capsules from the previous prescription. Remaining pills will be counted to determine compliance. The pharmacy will maintain records of receipt, dispensation, and return pill counts for compliance. Unused drug will be incinerated at the end of the study. On the day they pick up prescription refills, participants will report to the CRTU for a fasting blood sample to measure liver function (ALT, AST), coagulation (INR), blood lipid profile, glucose, and insulin. Participants will be withdrawn from the study if INR values exceed 2.0, indicating a high chance of bleeding. Participants will also be withdrawn from the study if ALT levels exceed 165IU/L or AST levels exceed 144IU/L. The duration of the intervention will be 6 months.

**Participants:** Our plan is to complete the study on 120 men and women age 65-85yrs and 30 young adults who will only be studied at baseline. We are anticipating a target accrual of 179 subjects to account for an anticipated dropout rate of 20% in the intervention group.

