**Exclusion criteria:**

- 1) Regular use of omega-3 nutritional supplements
- 2) Diabetes or fasting plasma glucose  $\geq 126$  mg/dL
- 3) Anemia (female subjects hemoglobin of  $\leq 11$  g/dL and male subjects hemoglobin  $\leq 12$  g/dL)
- 4) Active coronary artery disease or history of unstable macrovascular disease (unstable angina, myocardial infarction, stroke, and revascularization of coronary, peripheral or carotid artery within 3 months of recruitment)
- 5) Renal failure (serum creatinine  $> 1.5$  mg/dL)
- 6) Chronic active liver disease (AST  $> 144$  IU/L or ALT  $> 165$  IU/L)
- 7) Oral warfarin group medications or history of blood clotting disorders.
- 8) INR  $> 2.0$
- 9) Smoking
- 10) Pregnancy or breastfeeding
- 11) Alcohol consumption greater than 2 glasses/day or other substance abuse
- 12) Untreated or uncontrolled hypothyroidism
- 13) Debilitating chronic disease (at the discretion of the investigators)
- 14) Fish or shellfish allergy

**Consent and screening:** Potential participants will report to the Clinical Research and Trials Unit at Mayo Clinic Hospital St. Marys Campus the morning after an overnight fast. A member of the study team will meet the potential participant and the consent form will be read and discussed in private area. After receiving consent, the CRTU staff will measure vital signs including blood pressure, heart rate, temperature. Height and weight will be measured. The participant will undergo urine pregnancy test (if applicable) and screening blood work that will include CBC, lipid profile, creatinine, liver enzymes, TSH, glucose, insulin, blood clotting time (INR), c-reactive protein, and interleukin-6. Participants will be instructed on the use of a physical activity monitor (Actigraph), which they will wear for waking hours for a period of two weeks to quantify habitual physical activity levels. Participants will return for two additional blood draws and weight approximately 2 and 4 weeks later to repeat measurements of inflammatory markers (CBC, c-reactive protein, interleukin-6). Reconsenting may take place if study is stopped due to COVID closure. The subject will be withdrawn from the study at the point where the study stopped. The subject will be reconsented and start over from the beginning of the study.

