### Statistical analyses and Power:

For all variables in aim 1, the interest is in assessing if the change from baseline to post treatment differs by treatment arm. We will determine the influence of chronic inflammation on these outcomes in older adults grouped according to quartiles of a composite score including serum CRP and IL-6. The initial analysis will be stratified by inflammation composite score quartiles. Within a subgroup, the Wilcoxon rank sum test will be applied to test for difference in the change of outcome value pre and post treatment between the two treatment arms, placebo and n3-PUFAs. Additionally, generalized linear models will be used to assess the effect inflammation has on modifying the treatment effect by including interaction terms of a smoothing spline functional fit of the composite score with the treatment and time variables. The residuals from the regression will be used to assess distribution assumptions and variables will be transformed if required for appropriate statistical inference. All participants with at least a pre-treatment measurement will be included in the primary analysis utilizing the as-randomized study arm assignment for comparison. Efforts will be made to minimize missing data, but in the event of missing values, characteristics between those with observed values and with missing values will be compared. If no observed differences are identified, multiple imputation will be used with the primary analysis. Power calculations were performed for hypotheses related to mitochondrial physiology. We used the preliminary data where we measured effects of EPA on mitochondrial capacity. With mean  $JO_2 = 28.9 \text{ pmol/s/tissue}$  and  $\sigma = 4.891$ , a sample size of 15 per treatment group within an inflammation quartile gives 80% power ( $\alpha=0.05$ ) to detect a treatment difference in the difference from baseline to post treatment of  $5.18 \text{ pmol/s/tissue}$  (15% change). With 4 inflammation quartile groups, the total sample size will be 120, with

balanced randomization that gives 60 for each treatment arm in total. We believe that this expected difference is meaningful and realistic because our target population of older adults is known to exhibit reductions in mitochondrial capacity, and this degree of improvement would be physiologically important.

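### Crossing an INR, ALT or AST limit ends study participation rather than only softgel use, so some 6-month non-biopsy values may be lost needlessly (minor, cheap to fix)

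*Combined protocol and SAP*

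**What the plan says.** Section D, Study Design, has INR, ALT and AST checked at the refill visits every 4 weeks. For coagulation: "Participants will be withdrawn from the study if INR values exceed 2.0, indicating a high chance of bleeding". For liver enzymes: "Participants will also be withdrawn from the study if ALT levels exceed 165IU/L or AST levels exceed 144IU/L". No lesser step, such as stopping the softgels only, is described.

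The same paragraph schedules assessments that need no biopsy: "Before and after the intervention, all participants will complete an outpatient study day (body composition, blood draw, treadmill test, strength test" (the list ends there). Aim 1 fixes the time of the second measurement: "Outcomes will be measured again following 26 weeks of placebo or n3-PUFAs to reduce adipose tissue inflammation".

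Statistical analyses and Power defines the analysis set: "All participants with at least a pre-treatment measurement will be included in the primary analysis utilizing the as-randomized study arm assignment for comparison". The quantity compared is the change from before to after treatment. The section also promises efforts to keep missing data low. Where values are missing, "characteristics between those with observed values and with missing values will be compared", and multiple imputation follows if no differences are seen.

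On numbers, the Participants paragraph says: "We are anticipating a target accrual of 179 subjects to account for an anticipated dropout rate of 20% in the intervention group". The entry criteria exclude people above the same INR, AST and ALT limits, and also "Oral warfarin group medications or history of blood clotting disorders".

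**The concern.** Stopping a study product for safety and ending a participant's follow-up are different decisions. An as-randomised comparison needs the second measurement from everyone who can safely give it, whether or not they still take the product. Here one laboratory result triggers both decisions, so a participant willing to return at 6 months for a body composition scan, a blood draw or a strength test would, on the plain wording, not be asked.

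The trigger is a result obtained on treatment, so the missingness could in principle differ by arm and be related to outcome. At stake is the completeness of the non-biopsy endpoints in the comparison that the plan has already chosen.

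**Working it through.** **1. The texts side by side.** The Study Design wording ends participation. The consent and screening text uses the same expression for a COVID closure, after which the person is reconsented and starts again from the beginning; that supports reading it as a full stop. The statistical section wants a post-treatment value for everyone with a baseline value. Nothing in the text examined reconciles the two.

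**2. The plan's own figures.**
- Power: a two-sided two-sample t-test at 0.05 with SD 4.891, 15 per arm and a difference of 5.18 gives 79.9% power; the difference detectable at 80% is 5.183. The stated 80% is reproduced.
- Accrual: 120/(1 − 0.20) = 150, plus 30 young adults = 180, against 179 stated. This agrees to within one person.
- Older adults randomised: 179 − 30 = 149, or 149/2 = 74.5 per arm. Losses allowed for: 149 − 120 = 29 (29/149 = 19.5%).

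**3. How many people.** The documents give no rate, so these are assumptions applied to all 149:

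| Assumed rate | People affected |
|---|---|
| 0.5% | 0.7 |
| 1% | 1.5 |
| 2% | 3.0 |
| 5% | 7.5 |

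Even the last is 7.45/29 = 26% of the losses already allowed for. Were losses to go beyond that allowance, the power of one quartile comparison would fall from 79.9% to 78.4% (15 v 14) or 76.7% (15 v 13).

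**4. How large a shift.** Take 60 completers per arm, assume every affected person returns, and suppose that they would have changed by *d* SD less than completers. The shift removed is *d* times the arm difference in the share recovered.

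- *Equal rates, equal shortfall* (for example 2% in each arm): the share is 1.49/61.49 in both arms, so the shift is zero.
- *2% v 0%* (n3-PUFA v placebo): 0.02 × 74.5 = 1.49 people; 1.49/61.49 = 0.024.
- *5% v 2%*: 3.725 v 1.49 people, 5.2 in total; 3.725/63.725 − 1.49/61.49 = 0.0585 − 0.0242 = 0.034.

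Standard errors of an arm difference, in units of the SD of change: pooled √(2/60) = 0.183; within a quartile √(2/15) = 0.365.

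| Scenario | *d* | Shift (SD) | Share of pooled SE | Share of within-quartile SE |
|---|---|---|---|---|
| Equal rates | any | 0 | 0% | 0% |
| 2% v 0% | 0.5 | 0.012 | 7% | 3% |
| 2% v 0% | 1 | 0.024 | 13% | 7% |
| 5% v 2% | 0.5 | 0.017 | 9% | 5% |
| 5% v 2% | 1 | 0.034 | 19% | 9% |

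The within-quartile column is the yardstick for the initial analysis, which is stratified by quartile. The calculation is on the scale of means, as an approximation to the planned rank test. It ignores any imputation, so for the assumed rates and shortfalls it is an upper limit.

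**5. Precision.** With 61.49 v 60 the pooled standard error is 0.1815 SD (0.6% smaller than 0.1826). With 63.73 v 61.49 it is 0.1788 SD (2.1% smaller).

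**6. Time off softgels.** Stopping at a check in week 4, 8, 12, 16, 20 or 24, with outcomes at week 26, leaves 22, 18, 14, 10, 6 or 2 weeks off product. The mean is 12 if each check is equally likely.

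**The case against.** The strongest reply is that the rule is a sensible safety choice with little analytic consequence. An INR above 2.0 is a reason not to take muscle and fat biopsies, place catheters or draw about 407 mL of blood, and the same limits bar entry. The powered endpoint, JO2, comes from muscle biopsy. Two of the three main Aim 2 outcomes also need muscle, and the third needs the inpatient tracer infusion. A mechanistic study of 26 weeks on product may also have little use for values taken after weeks off it.

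Most of this stands. The limits are not in question, and biopsy endpoints may well stay missing. But body composition, a blood draw and, where permitted, strength testing carry no biopsy risk, and the plan itself chose an as-randomised analysis. The off-product values fit that choice and can be left out of a sensitivity analysis.

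A reader might infer three stronger things that the documents do not support:

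- *That the rule biases the treatment comparison.* No event rate or arm difference is given, and with equal rates and equal shortfall the shift vanishes. Entry criteria that exclude the same limits and warfarin-type drugs make events likely to be few.
- *That it threatens power.* The losses fit within the 20% allowance.
- *That it causes the gap in the imputation plan.* Making imputation conditional on seeing no differences affects every dropout and is a separate matter.

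**Conclusion.** The point holds as a low-severity improvement. The wording ends study participation where stopping softgels would do, and it sits awkwardly with the plan's as-randomised analysis of change and its promise to minimise missing data.

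The size depends wholly on assumed rates: about 1 to 7 people, and a shift from about zero to about 0.03 SD on non-biopsy endpoints, always well below one standard error. The non-zero figures further assume more withdrawals on n3-PUFA and a shortfall of half to one SD in those withdrawn.

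It would go too far to say that the 6-month values are definitely not collected. The data and safety monitoring plan and a few parts of the protocol were not in the text examined, and they may provide for follow-up. If they do, the Study Design wording should be brought into line with them.

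**What to change.** In Study Design, replace withdrawal from the study with: *permanently discontinued from softgels, with follow-up continued unless consent is withdrawn*. Then state that:

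- the scheduled 6-month non-biopsy assessments that the investigator judges safe will be done: at least body composition and the blood draw, with strength, treadmill and other tests where permitted;
- biopsies will be done only if INR and liver tests allow at that time;
- the values will be analysed in the randomised arm;
- the stop date and reason will be recorded, so that an on-treatment sensitivity analysis can exclude values obtained off softgels.

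The INR, ALT and AST limits do not change.

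The cost is a short change to protocol and consent wording, and a few more people seen at visits already in the design. The downside is that off-softgel values dilute an on-treatment effect, which is why the stop date must be recorded.

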#### **Description of recruitment methods:**

We will use lists of prior research participants in our lab who have given permission to be contacted. We will use brochures, flyers, radio ads, television ads, and advertisements on the Research Studies section of the Mayo Classifieds. A member of the study team will contact participants by telephone or email with a brief description of the study and to determine if they are interested in participating. Brochures, flyers and radio ads will include the telephone number of a study team member. Participants will be asked to call the contact person. When the call is received, the member of the study team will perform a brief screening questionnaire to determine eligibility to proceed with enrollment. The screening questionnaire may also be sent by email in accordance with the Research Policy Manual Policy on Electronic Communications with Research

Subjects. The information gathered from the screening questionnaire will not be stored or used for data analysis if participants do not qualify for the study.

